**9.4.3 Pharmacokinetic Analyses**

Analyses will be carried out on the PK analysis population.

Individual and mean plasma concentrations at each sampling time-point for RO7049389 and its metabolites (RO7121986, RO7255420 and RO7255422), pitavastatin and pitavastatin lactone as appropriate will be presented by listings and descriptive summary statistics, including means, geometric means, ranges, standard deviations and coefficients of variation. Individual and mean concentration versus time will be plotted on semi-logarithmic scales.

Non-compartmental analysis will be employed for estimation of PK parameters. All PK parameters will be presented by individual listings and summary statistics for each period including means, geometric means, medians, ranges, standard deviations and coefficients of variation.

To assess the effect of RO7049389 on the PK of pitavastatin, the logarithmically transformed variables  $C_{max}$  and  $AUC_{0-inf}$  of pitavastatin and its metabolite pitavastatin lactone will be subjected to an ANOVA (with factors RO7049389 and participant) for which measurements are available for healthy participants in both with/without

RO7049389. 90% confidence intervals for the ratio of geometric means will be calculated using the pitavastatin alone as the reference.

The same analysis of variance will be applied to the secondary parameters  $AUC_{0-12hr}$  and  $C_{max}$  of RO7049389 and its metabolites (RO7121986, RO7255420 and RO7255422) to assess the effect of pitavastatin on the PK of RO7049389.

In case  $AUC_{0-inf}$  cannot be determined reliably, an appropriately truncated AUC will be used.

#### **9.4.4            Pharmacodynamic Analyses**

Not Applicable.

#### **9.4.5            Other Analyses**

Individual ratios (before and after 3 days of RO7049389 treatment) of coproporphyrins (CP-I and CP-III) will be listed and summarized using descriptive statistics. Geometric mean ratio of after RO7049389 treatment relative to before RO7049389 treatment and the 90% confidence intervals will be computed.

### **9.5                SUMMARIES OF CONDUCT OF STUDY**

The number of participants who enroll, discontinue, or complete the study will be summarized. Reasons for premature study withdrawal will be listed and summarized by treatment period. Protocol deviations will be listed and evaluated for their potential impact on interpretation of study results. Study drug administration will be summarized by treatment period. Descriptive statistics will be used in evaluating the conduct of the study.

**11. SUPPORTING DOCUMENTATION AND OPERATIONAL CONSIDERATIONS**

The following section includes standard appendices such as [Appendix 1](#) (for regulatory, ethical and study oversight considerations), [Appendix 2](#) (for AE definitions, reporting) and [Appendix 3](#) (procedures of recording), [Appendix 5](#) (contraceptive guidance and collection of pregnancy information). Additional study-related appendices are in order of appearance in the protocol.

## **Appendix 1**

### **Regulatory, Ethical, and Study Oversight Considerations**

#### **1. REGULATORY AND ETHICAL CONSIDERATIONS**

##### **1.1. COMPLIANCE WITH LAWS AND REGULATIONS**

This study will be conducted in full conformance with the ICH E6 guideline for Good Clinical Practice and the principles of the Declaration of Helsinki, or the laws and regulations of the country in which the research is conducted, whichever affords the greater protection to the individual. The study will comply with the requirements of the ICH E2A guideline (Clinical Safety Data Management: Definitions and Standards for Expedited Reporting). Studies conducted in the United States or under a U.S. Investigational New Drug (IND) application will comply with U.S. FDA regulations and applicable local, state, and federal laws. Studies conducted in the EU/EEA will comply with the EU Clinical Trial Directive (2001/20/EC).

##### **1.2. INSTITUTIONAL REVIEW BOARD OR ETHICS COMMITTEE**

This protocol, the ICFs, any information to be given to the participant (e.g. advertisements, diaries etc), and relevant supporting information must be submitted to the IRB/EC by the Principal Investigator and reviewed and approved by the IRB/EC before the study is initiated. In addition, any participant recruitment materials must be approved by the IRB/EC.

The Principal Investigator is responsible for providing written summaries of the status of the study to the IRB/EC annually or more frequently in accordance with the requirements, policies, and procedures established by the IRB/EC. Investigators are also responsible for promptly informing the IRB/EC of any protocol amendments (Section 2.3.1 of this Appendix).

The Investigator should follow the requirements for reporting all adverse events to the Sponsor. Investigators may receive written IND safety reports or other safety-related communications from the Sponsor. Investigators are responsible for ensuring that such reports are reviewed and processed in accordance with Health Authority requirements and the policies and procedures established by their IRB/EC, and archived in the site's study file.

##### **1.3. INFORMED CONSENT**

The Sponsor's Master Informed Consent Form (and ancillary sample ICFs such as a Child's Assent or Caregiver's Informed Consent Form, if applicable) will be provided to each site. If applicable, it will be provided in a certified translation of the local language. Participants must be informed that their participation is voluntary. Participants will be required to sign a statement of informed consent that meets the requirements of 21 CFR 50, local regulations, ICH guidelines, where applicable, and the IRB/IEC or study center. The Sponsor or its designee must review and approve any proposed deviations from the

Sponsor's sample ICFs or any alternate consent forms proposed by the site (collectively, the "Consent Forms") before IRB/EC submission. The final IRB/EC-approved Consent Forms must be provided to the Sponsor for Health Authority submission purposes according to local requirements. Participants must be re-consented to the most current version of the ICF(s) during their participation in the study. A copy of the ICF(s) signed by all parties must be provided to the participant or the participant's legally authorized representative.

The Consent Forms must be signed and dated by the participant before his or her participation in the study. The case history or clinical records for each participant shall document the informed consent process and that written informed consent was obtained prior to participation in the study.

The Consent Forms should be revised whenever there are changes to study procedures or when new information becomes available that may affect the willingness of the participant to take part. The final revised IRB/EC-approved Consent Forms must be provided to the Sponsor for Health Authority submission purposes if required as per local regulations.

Participants must be re-consented to the most current version of the Consent Forms (or to a significant new information/findings addendum in accordance with applicable laws and IRB/EC policy) during their participation in the study. For any updated or revised Consent Forms, the case history or clinical records for each participant shall document the informed consent process and that written informed consent was obtained using the updated/revised Consent Forms for continued participation in the study.

A copy of each signed Consent Form must be provided to the participant or the participant's legally authorized representative. All signed and dated Consent Forms must remain in each participant's study file or in the site file and must be available for verification by study monitors at any time.

### **Consent to Participate in the Research Biosample Repository**

The ICF will contain a separate section that addresses participation in the RBR. The Investigator or authorized designee will explain to each participant the objectives, methods, and potential hazards of participation in the RBR. Participants will be told that they are free to refuse to participate and may withdraw their specimens at any time and for any reason during the storage period. A separate, specific signature will be required to document a participant's agreement to provide optional RBR specimens. Participants who decline to participate will not provide a separate signature.

The Investigator should document whether or not the participant has given consent to participate by completing the RBR Sample Informed Consent eCRF.

In the event of death or loss of competence of a subject who is participating in the Research, the participant's specimens and data will continue to be used as part of the RBR.

If the site utilizes a separate Authorization Form for patient authorization for use and disclosure of personal health information, the review, approval, and other processes outlined above apply except that IRB review and approval may not be required per study site policies.

### **Approval by the Institutional Review Board or Ethics Committee**

Sampling for the RBR is contingent upon the review and approval of the exploratory research and the RBR portion of the ICF by each site's Institutional Review Board or Ethics Committee (IRB/EC) and, if applicable, an appropriate regulatory body. If a site has not been granted approval for RBR sampling, this section of the protocol will not be applicable at that site

### **Withdrawal from the Research Biosample Repository**

Participants who give consent to provide specimens for the RBR have the right to withdraw their specimens at any time for any reason. If a participant wish to withdraw consent to the testing of his or her specimens, the Investigator must inform the Medical Monitor in writing of the participant's wishes using the RBR Withdrawal Form and, if the trial is ongoing, must enter the date of withdrawal on the RBR Withdrawal of Informed Consent eCRF. The participant will be provided with instructions on how to withdraw consent after the trial is closed. A participant's withdrawal from Study YP40218 does not, by itself, constitute withdrawal of specimens from the RBR. Likewise, a participant's withdrawal from the RBR does not constitute withdrawal from Study YP40218. Data already generated before time of withdrawal of consent to RBR will still be used.

## **1.4. CONFIDENTIALITY**

Participants will be assigned a unique identifier by the Sponsor. Any participant records or datasets that are transferred to the Sponsor will contain the identifier only; participant names or any information which would make the participant identifiable will not be transferred.

The participant must be informed that his/her personal study-related data will be used by the Sponsor in accordance with local data protection law. The level of disclosure must also be explained to the participant.

Medical information may be given to a participant's personal physician or other appropriate medical personnel responsible for the participant's welfare, for treatment purposes.

The participant must be informed that his/her medical records may be examined by Clinical Quality Assurance auditors or other authorized personnel appointed by the sponsor, by appropriate IRB/IEC members, and by inspectors from regulatory authorities.

## **1.5. FINANCIAL DISCLOSURE**

Investigators will provide the Sponsor with sufficient, accurate financial information in accordance with local regulations to allow the Sponsor to submit complete and accurate financial certification or disclosure statements to the appropriate Health Authorities. Investigators are responsible for providing information on financial interests during the course of the study and for one year after completion of the study (i.e., LPLV).

## **2. DATA HANDLING AND RECORD**

### **2.1. DATA COLLECTION AND MANAGEMENT RESPONSIBILITIES**

#### **2.1.1. Data Quality Assurance**

All participant data relating to the study will be recorded on printed or electronic CRF unless transmitted to the Sponsor or designee electronically (e.g., laboratory data). The Investigator is responsible for verifying that data entries are accurate and correct by physically or electronically signing the CRF.

The Investigator must maintain accurate documentation (source data) that supports the information entered in the CRF.

The Investigator must permit study-related monitoring, audits, IRB/IEC review, and regulatory agency inspections and provide direct access to source data documents.

The Sponsor or designee is responsible for the data management of this study including quality checking of the data.

Study monitors will perform ongoing source data verification to confirm that data entered into the CRF by authorized site personnel are accurate, complete, and verifiable from source documents; that the safety and rights of participants are being protected; and that the study is being conducted in accordance with the currently approved protocol and any other study agreements, ICH GCP, and all applicable regulatory requirements.

#### **2.1.3. Source Data Records**

Source documents (paper or electronic) are those in which participant data are recorded and documented for the first time. They include, but are not limited to, hospital records, clinical and office charts, laboratory notes, memoranda, COAs (paper or eCOA), evaluation checklists, pharmacy dispensing records, recorded data from automated instruments, copies of transcriptions that are certified after verification as being accurate and complete, microfiche, photographic negatives, microfilm or magnetic media, X-rays, patient files, and records kept at pharmacies, laboratories, and medico-technical departments involved in a clinical trial.

Before study initiation, data to be entered directly into the eCRFs (i.e., no prior written or electronic record of the data) and considered source data must be defined in the Trial Monitoring Plan.

Source documents that are required to verify the validity and completeness of data entered into the eCRFs must not be obliterated or destroyed and must be retained per the policy for retention of records described below.

To facilitate source data verification, the Investigators and institutions must provide the Sponsor direct access to applicable source documents and reports for trial-related monitoring, Sponsor audits, and IRB/EC review. The investigational site must also allow inspection by applicable Health Authorities.

#### **2.1.4. Use of Computerized Systems**

When clinical observations are entered directly into an investigational site's computerized medical record system (i.e., in lieu of original hardcopy records), the electronic record can serve as the source document if the system has been validated in accordance with Health Authority requirements pertaining to computerized systems used in clinical research. An acceptable computerized data collection system allows preservation of the original entry of data. If original data are modified, the system should maintain a viewable audit trail that shows the original data as well as the reason for the change, name of the person making the change, and date of the change.

### **2.2. RETENTION OF RECORDS**

Records and documents, including signed ICF, pertaining to the conduct of this study must be retained by the Investigator for at least 15 years after study completion unless local regulations or institutional policies require a longer retention period. No records may be destroyed during the retention period without the written approval of the Sponsor. No records may be transferred to another location or party without written notification to the Sponsor.

### **2.3. STUDY RECORDS**

The Investigator must maintain adequate and accurate records to enable the conduct of the study to be fully reconstructed, including but not limited to the protocol, protocol amendments, ICFs, and documentation of IRB/EC and governmental approval.

#### **2.3.1. Protocol Amendments**

Any substantial protocol amendments will be prepared by the Sponsor. Substantial protocol amendments will be submitted to the IRB/EC and to regulatory authorities in accordance with local regulatory requirements.

Approval must be obtained from the IRB/EC and regulatory authorities (as locally required) before implementation of any changes, except for changes necessary to

eliminate an immediate hazard to patients or any non-substantial changes, as defined by regulatory requirements.

### **2.3.2. Publication Policy**

The results of this study may be published or presented at scientific meetings. If this is foreseen, the Investigator agrees to submit all manuscripts or abstracts to the Sponsor for approval prior to submission. This allows the Sponsor to protect proprietary information and to provide comments based on information from other studies that may not yet be available to the Investigator.

The Sponsor will comply with the requirements for publication of study results. In accordance with standard editorial and ethical practice, the Sponsor will generally support publication of multicenter trials only in their entirety and not as individual center data. In this case, a coordinating Investigator will be designated by mutual agreement.

Any formal publication of the study in which contribution of Sponsor personnel exceeded that of conventional monitoring will be considered as a joint publication by the Investigator and the appropriate Sponsor personnel.

Authorship will be determined by mutual agreement and in line with International Committee of Medical Journal Editors authorship requirements.

Any inventions and resulting patents, improvements, and/or know-how originating from the use of data from this study will become and remain the exclusive and unburdened property of the Sponsor, except where agreed otherwise.

### **2.3.3. Dissemination of Clinical Study Data**

A clinical study report containing the results of this trial will be made available to anyone who requests a copy. A description of this clinical trial and a summary of its results will be available at <http://www.ClinicalTrials.gov>.

### **2.3.4. Site Inspections**

Site visits will be conducted by the Sponsor or an authorized representative for inspection of study data, participants' medical records, and eCRFs. The Investigator will permit national and local Health Authorities, Sponsor monitors, representatives, and collaborators, and the IRBs/ECs to inspect facilities and records relevant to this study.

## **3. ADMINISTRATIVE STRUCTURE**

The Sponsor of the trial is F. Hoffmann-La Roche Ltd. The Sponsor is responsible for the study management, data management, statistical analysis and medical writing for the clinical study report.

#### **4. STUDY AND SITE CLOSURE**

The Sponsor (or designee) has the right to close the study site or terminate this study at any time. Reasons for terminating the study may include, but are not limited to, the following:

- The incidence or severity of adverse events in this or other studies indicates a potential health hazard to participants.
- Participant enrollment is unsatisfactory.

The Sponsor will notify the Investigator and Health Authorities if the study is placed on hold, or if the Sponsor decides to discontinue the study or development program.

The study site will be closed upon study completion. A study site is considered closed when all required documents and study supplies have been collected and a study-site closure visit has been performed.

The Investigator may initiate study-site closure at any time, provided there is reasonable cause and sufficient notice is given in advance of the intended termination.

Reasons for the early closure of a study site by the Sponsor or Investigator may include but are not limited to:

- Failure of the Investigator to comply with the protocol, the requirements of the IRB/IEC or local Health Authorities, the Sponsor's procedures, or GCP guidelines.
- Inadequate recruitment of participants by the Investigator.
- Discontinuation of further study treatment development.

## **Appendix 2**

### **Adverse Events: Definitions and Procedures for Evaluating, Follow-up and Reporting**

#### **1. DEFINITION OF ADVERSE EVENTS**

According to the E2A ICH guideline for Good Clinical Practice, an **adverse event** is any untoward medical occurrence in a patient or clinical investigation subject administered a pharmaceutical product and which does not necessarily have to have a causal relationship with this treatment.

An adverse event can therefore be:

- Any unfavorable and unintended sign (including an abnormal laboratory finding), symptom, or disease temporally associated with the use of a medicinal product, whether or not considered related to the medicinal product.

#### **Events Meeting the AE Definition:**

- Any deterioration in a laboratory value (hematology, clinical chemistry, or urinalysis) or other clinical test (e.g., ECG, X-ray) that is associated with symptoms or leads to a change in study treatment or concomitant treatment or discontinuation from study treatment.
- Exacerbation of a chronic or intermittent pre-existing condition, including either an increase in frequency and/or intensity of the condition.
- New conditions detected or diagnosed after study treatment administration even though it may have been present before the start of the study.
- Adverse events that are related to a protocol-mandated intervention, including those that occur prior to assignment of study treatment (e.g., screening invasive procedures such as biopsies).

#### **Events NOT Meeting the AE Definition:**

- Any clinically significant abnormal laboratory findings or other abnormal safety assessments, unless judged by the Investigator to be more severe than expected for the participant's condition.
- Medical or surgical procedure (e.g., endoscopy, appendectomy): the condition that leads to the procedure is an AE.
- Situations where an untoward medical occurrence did not occur (social and/or convenience admission to a hospital).

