#### **8.2.4 Clinical Safety Laboratory Assessments**

Normal ranges for the study laboratory parameters must be supplied to the Sponsor before the study starts. A list of clinical laboratory tests to be performed is provided in [Appendix 4](#) and these assessments must be conducted in accordance with the separate laboratory manual and the SoA (Section 1.3).

The Investigator must review the laboratory report, document this review, and record any clinically relevant changes occurring during the study in the AE section of the CRF. The laboratory reports must be filed with the source documents. Clinically significant abnormal laboratory findings are those which are not associated with the underlying disease, unless judged by the Investigator to be more severe than expected for the participant's condition.

- In the event of unexplained abnormal clinically significant laboratory test values, the tests should be repeated immediately and followed up until they have returned to the normal range and/or an adequate explanation of the abnormality is found.
- If such values do not return to normal/baseline within a period of time judged reasonable by the Investigator, the etiology should be identified and the Sponsor notified.
- If laboratory values from non-protocol specified laboratory assessments performed at the local laboratory require a change in participant management or are considered clinically significant by the Investigator (e.g., SAE or AE or dose-modification) then, the results must be recorded in the CRF.

Results of clinical laboratory testing will be recorded on the eCRF or be received as electronically produced laboratory reports submitted directly from the local laboratory.

Additional blood or urine samples may be taken at the discretion of the Investigator if the results of any test fall outside the reference ranges, or clinical symptoms necessitate additional testing to monitor participant safety.

Where the clinical significance of abnormal lab results is considered uncertain, screening lab tests may be repeated prior to enrollment to confirm eligibility.

If there is an alternative explanation for a positive urine or blood test for drugs of abuse, e.g., previous occasional intake of a medication or food containing for example, codeine, benzodiazepines or opiates, the test could be repeated to confirm washout.

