#### **4. ABNORMAL LABORATORY VALUES**

Not every laboratory abnormality qualifies as an adverse event. A laboratory test result should be reported as an adverse event if it meets any of the following criteria:

- Accompanied by clinical symptoms.
- Results in a change in study treatment (e.g., dosage modification, treatment interruption, or treatment discontinuation).
- Results in a medical intervention (e.g., potassium supplementation for hypokalemia) or a change in concomitant therapy.
- Clinically significant in the Investigator's judgment.

It is the Investigator's responsibility to review all laboratory findings. Medical and scientific judgment should be exercised in deciding whether an isolated laboratory abnormality should be classified as an adverse event.

If a clinically significant laboratory abnormality is a sign of a disease or syndrome (e.g., alkaline phosphatase and bilirubin 5 times the upper limit of normal [ULN] associated with cholecystitis), only the diagnosis (i.e., cholecystitis) should be recorded on the Adverse Event eCRF.

If a clinically significant laboratory abnormality is not a sign of a disease or syndrome, the abnormality itself should be recorded on the Adverse Event eCRF, along with a descriptor indicating if the test result is above or below the normal range (e.g., "elevated potassium", as opposed to "abnormal potassium"). If the laboratory abnormality can be characterized by a precise clinical term per standard definitions, the clinical term should be recorded as the adverse event. For example, an elevated serum potassium level of 7.0 mEq/L should be recorded as "hyperkalemia".

Observations of the same clinically significant laboratory abnormality from visit to visit should not be repeatedly recorded on the Adverse Event eCRF, unless the etiology changes. The initial severity of the event should be recorded, and the severity or seriousness should be updated any time the event worsens.

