## **5. ABNORMAL VITAL SIGN VALUES**

Not every vital sign abnormality qualifies as an adverse event. A vital sign result should be reported as an adverse event if it meets any of the following criteria:

- Accompanied by clinical symptoms.
- Results in a change in study treatment (e.g., dosage modification, treatment interruption, or treatment discontinuation).
- Results in a medical intervention or a change in concomitant therapy.
- Clinically significant in the Investigator's judgment.

It is the Investigator's responsibility to review all vital sign findings. Medical and scientific judgment should be exercised in deciding whether an isolated vital sign abnormality should be classified as an adverse event.

If a clinically significant vital sign abnormality is a sign of a disease or syndrome (e.g., high blood pressure), only the diagnosis (i.e., hypertension) should be recorded on the Adverse Event eCRF.

Observations of the same clinically significant vital sign abnormality from visit to visit should not be repeatedly recorded on the Adverse Event eCRF, unless the etiology changes. The initial severity of the event should be recorded, and the severity or seriousness should be updated any time the event worsens.

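### Appendix 2 excludes clinically significant abnormal findings from the AE definition by default, while Appendix 3 and Section 8.2.1 make clinical significance enough for an AE; the rules give opposite answers in one narrow case

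*Combined protocol and SAP*

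**What the plan says.** Appendix 2, Section 1 has two lists. The list of events that meet the AE definition includes a deterioration in a laboratory value or other clinical test "that is associated with symptoms or leads to a change in study treatment or concomitant treatment or discontinuation from study treatment". The list of events that do not meet it opens with "Any clinically significant abnormal laboratory findings or other abnormal safety assessments, unless judged by the Investigator to be more severe than expected". The yardstick for that exception is the participant's condition.

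Appendix 3, Section 4 starts from the other side: "A laboratory test result should be reported as an adverse event if it meets any of the following criteria". The fourth criterion is "Clinically significant in the Investigator's judgment". It then adds: "If a clinically significant laboratory abnormality is not a sign of a disease or syndrome, the abnormality itself should be recorded on the Adverse Event" page of the eCRF.

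Appendix 3, Section 5 does the same for vital signs ("A vital sign result should be reported as an adverse event if it meets any of the following criteria"), with the same fourth criterion. Section 8.2.1 sends new or worsened physical findings of clinical significance to the Adverse Event eCRF.

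Section 8.2.4 tells the Investigator to "record any clinically relevant changes occurring during the study in the AE section of the CRF". It also offers a definition: "Clinically significant abnormal laboratory findings are those which are not associated with the underlying disease", followed by the same kind of exception as in Appendix 2.

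Section 8.3 refers the Investigator to Appendix 2 for what an AE is and to Appendix 3 for how to record one. Neither is said to override the other.

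**The concern.** The same attribute, clinical significance as judged by the Investigator, keeps a finding out of the AE count by default in one appendix and brings it in under the other. AE incidence and severity is a secondary endpoint (Section 3, Table 3), and Section 9.4.2, Table 6 groups AEs by treatment period. If staff follow different appendices, or one person follows different appendices in different periods, the descriptive comparison of pitavastatin alone with the combination partly reflects which rule was used.

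The kind of finding at issue is realistic here. Section 2.2.3 reports elevated hepatic enzymes at 0.0% to 8.8% with pitavastatin, and the dose rationale in Section 4 says that an OATP1B1-mediated rise in exposure cannot be ruled out. Safety laboratory samples are taken on Period 2 Day 7 and at the follow-up visit, after the last RO7049389 dose on Day 6. At those visits no study dosing is left to change, so an asymptomatic abnormality can qualify under the laboratory item of Appendix 2's positive list only through a change in concomitant treatment.

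**Working it through.** The plan gives no figure to reproduce. The check sets the rules side by side and asks, for each kind of abnormal finding, whether they agree.

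| Finding | Appendix 2, Section 1 | Appendix 3, Sections 4–5 | Agree? |
|---|---|---|---|
| A. With symptoms, or leading to a change in study or concomitant treatment | AE (positive list) | AE | Yes |
| B. Clinically significant, no symptoms, no treatment change, judged worse than expected | Exception applies, so not excluded | AE | Yes |
| C. Clinically significant, no symptoms, no treatment change, not judged worse than expected | Not an AE | AE | **No** |

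The conflict is therefore confined to case C. For physical findings the contrast is with Section 8.2.1 and is the same: the Appendix 2 bullet covers other abnormal safety assessments as well as laboratory results.

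**What separates B from C.** The boundary is whether a finding is worse than the participant's condition would lead one to expect. Section 5.1, criterion 3 defines participants by the absence of active or chronic disease. There is no disease course to supply an expected severity, and the protocol gives no other yardstick. Two Investigators could place the same result in different rows without either departing from the text.

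**Reach into SAEs.** Appendix 2, Section 2 says that an event outside the AE definition cannot be serious, even when a seriousness criterion is met. A case C finding excluded under Section 1 is thereby also barred from SAE status, whereas under Appendix 3 it is an AE and can be assessed for seriousness.

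**Weight of one participant.** The planned number is 18 enrolled and 16 evaluable (Section 5).
- Change in AE incidence = 1/N for a participant whose only AE is a case C finding.
- N = 18: 1/18 = 0.0556, or 5.6 percentage points.
- N = 16: 1/16 = 0.0625, or 6.3 percentage points.
- A participant who already has another AE in the same summary changes it by 0 points.

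Because AEs are grouped by treatment period, the denominator is the number treated in that period and may differ from 18. The documents do not give the expected number of case C participants. The 0.0% to 8.8% range does not supply it, since it is not split by symptoms or clinical significance.

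**The case against.** The strongest reply is that the exception closes the gap. Participants are healthy by definition, and Section 5.2, criterion 17 excludes clinically significant laboratory abnormalities at screening or Day -1. Against that baseline, any new clinically significant result could be called worse than expected. Every finding would then fall in row B and the rules would agree. This is a sensible reading and may be what was meant, but the protocol does not state it. It would also leave the exclusion bullet with nothing to exclude.

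A second reply is that Section 8.3 names abnormal laboratory values among the topics covered by Appendix 3, so the more specific instruction favours recording, and Section 8.2.4 points the same way. That helps in practice. However, Section 8.3 also makes Appendix 2 the source of the definition, so precedence remains unstated.

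Some stronger readings are tempting, and the documents do not support them:
- A reader might infer that the two appendices count all laboratory AEs by opposite rules. They agree in rows A and B, and Appendix 2 itself opens by naming an abnormal laboratory finding as a possible AE.
- A reader might infer that an isolated liver-enzyme rise would disappear from the report. Laboratory abnormalities are a separate secondary endpoint, flagged from reference ranges regardless of AE status (Table 6 and Appendix 4). Appendix 3, Section 6 also requires AE reporting of ALT or AST above 3 × ULN combined with bilirubin above 2 × ULN or jaundice.
- A reader might treat Section 8.2.4 as a third conflicting rule. Its reference to an underlying disease has nothing to act on in healthy volunteers. It is loose wording and weaker evidence than Appendix 3.

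**Conclusion.** The inconsistency is in the current text and should be corrected, but it is narrow. The rules give opposite answers only for an isolated, asymptomatic, clinically significant laboratory, vital-sign or physical finding, with no change in study or concomitant treatment, that the Investigator does not judge worse than expected. In that case it affects AE incidence and, through Appendix 2, Section 2, SAE classification. The primary PK endpoints and the laboratory-abnormality endpoint are untouched, and the safety summaries are descriptive with no hypothesis test.

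The size is 5.6 points of AE incidence with 18 participants, or 6.3 with 16, for each participant whose sole AE is of this kind. It should not be read as a shift for every such finding: a second finding in the same participant adds nothing. The conclusion assumes that Investigators may apply Appendix 2 as written. If all of them treated any clinically significant finding in a healthy person as worse than expected, the practical effect would be nil, but the protocol does not tell them to.

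**What to change.** Reconcile the passages before AE data are collected. Delete the first bullet under *Events NOT Meeting the AE Definition* in Appendix 2, Section 1, or reword it so that it agrees with Appendix 3, Sections 4 and 5, and state that those sections are the single recording rule for abnormal laboratory and vital-sign results. Section 8.2.1 already agrees with that rule for physical findings. Removing the sentence on underlying disease from Section 8.2.4 is optional tidying.

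The change takes a sentence or two and possibly leads to a few more recorded AEs. Visits, samples, sample size and the PK analysis stay as they are.
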